# **1.1 Specific Aims and Hypotheses are:**

Aim 1: To evaluate the feasibility (including facilitators and barriers to use) and satisfaction of computerized cognitive training delivered in the home among BCS.

**Hypothesis 1**: BCS assigned to the cognitive training arm will perceive the intervention as more acceptable and useful than BCS assigned to the attention control condition.

Aim 2: To test the preliminary efficacy of the cognitive training intervention for improving perceived cognitive function over time compared to attention control.

**Hypothesis 2.1**: The intervention group will have greater improvement in subjectively measured cognitive function (Perceived cognitive impairment and Perceived cognitive capabilities) over time compared to attention control.

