#### 8.2 Intervention

The baseline assessment will be completed and then the participant will be randomized to computerized cognitive training or attention control group. An immediate post-test will be

completed, which will be 10 weeks after baseline (10 weeks for intervention within 90 days for completing the post-intervention assessment). The first visit will last about 1-hour and all other visits should last about 50 minutes.

At baseline, participants will provide demographic, clinical and treatment information, questionnaire data, blood sample, and complete a neuropsychological assessment administered by a trained and blinded tester. All other assessments will proceed in the same manner; however, demographic and treatment information will not be re-assessed. The medical record of BCS's will be examined for purposes of verifying disease and treatment information, including types and dates of treatments received (surgery, radiation, chemotherapy, tamoxifen and/or aromatase inhibitors). Data will be linked to participants through the use of a unique study-specific identifying number. Only persons on the research team will have access to the data. The neuropsychological tester will remain blinded to the randomization of the participants. All data are collected for research purposes only.

**Cognitive Training:** As tested in our pilot, the Brain HQ program is designed to enhance specific areas of cognitive functioning that will be tested in this study. The goals of the Brain HQ program are to improve visual processing speed, learning and memory and attention. The exercises include time-order judgment, discrimination, spatial-match, forward-span, instruction-following, and narrative-memory tasks. This program systematically reduces the stimulus duration during a series of increasingly difficult information-processing tasks presented via computer. The exercises automatically adjust to user performance to maintain an 85% correct rate. The program will include 4 hours per week over a 10-week period for a total of up to 40 hours. We have support from the original developer and Posit Science. For the purposes of this trial, any participants who do not complete the total of up to 40 hours will not be counted as deviations.

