**Attention Control:** Control participants will be asked to complete activities on the computer. The program offers a choice of activities that will consist of crossword puzzles and word jumbles. Attention Control: Computer-based General Cognitive Stimulation Intervention (Computerized Crossword Puzzles): The program offers a pre-determined set of computerized crossword puzzles (www.bestcrosswords.com; http://zone.msn.com/en/crossword; Accessed *09-15-2015*). The site has over 100,000 puzzles and can be accessed easily via the web and are free to users. The computerized crossword puzzles do not provide for progressive challenges of increasing speed, visual field size, number of distractors or degree of difficulty of targeted stimulus differentiation. Training: Participants will be instructed to perform this active attention control intervention 4 hours per week over 10 weeks for a total of up to 40 hours, the same as BrainHQ.

The rationale for this attention control program is (1) it has been routinely and successfully used in other NIH-funded cognitive training trials, (2) it has not shown cognitive benefit in previous research studies, and (3) previous experience by our team and others have shown that it is an appropriate computerized attention control alternative. The delivery format, number of sessions, and setting all parallel the intervention of up to 40 hours over 10 week period. Table 1 describes the difference between the **Brain HQ** intervention and the attention control cognitive training interventions.

Table 1 Comparison of BrainHQ to Attention Control						
Element	Computerized Cognitive Training using BrainHQ	Attention Control Computer-Based General Cognitive	amount required.			
Visual stimuli	Intensive & repetitive with increasing visual stimuli	None	control			
Complexity of stimuli	Progressively increased speed & processing of stimuli with increasing distractions	No Progressive Challenge	the partic in the stu			
Cognitive demand	Tailored; Training adjusted by computer to 85% of individual's threshold	Not tailored; not adjusted or tailored for individual threshold	follow up be condu post in Based or			
Visual attention & memory	Directed attention with each exercise, precision	No directed attention from computerized intervention	the assessme			

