Novelty	Individualized feedback and rewards built in to respond to the participant, game features to improve satisfaction	Feedback and rewards not provided, may incur some satisfaction on their own	complete of co interventi attention			

Based on the randomization, the project manager will provide verbal and written instruction for

accessing and using the program and the minimum amount of practice required. BrainHQ and computerized attention control programs will capture the date and time the participants participate in the study.

ntervention: Α assessment will icted immediately tervention (T2). n our pilot study, post-intervention ent and BDNF draw will be d within 90 days ompleting the on (T2) training or control sessions.

edures for

Monitoring Treatment Fidelity: As in our pilot, procedures for monitoring treatment fidelity will

be guided by the Treatment Fidelity Checklist. Both groups have been standardized in dose (length and content) and delivery method (in-home). Intervention dose will be carefully monitored using the computer software built within BrainHQ and Rescue Time software for the active attention control (total time on task). These variables will be examined and used in the analysis. The PI will be responsible for oversight of treatment fidelity The neuropsychological tester will be blinded to group status. The project manager will ensure the participants understand and are utilizing the program. Treatment dose and content will be carefully monitored through the InSight program.

**Qualitative assessment**: individual interviews will be conducted over the phone with members of the intervention group to understand the perceived facilitators and barriers to use of the intervention. All interviews will be conducted after the intervention, voice recorded digitally and labeled with a patient identification number.

Accrual & Retention: Several steps will be taken to ensure high rates of accrual, retention, and representation of minority BCS. These include (1) using culturally appropriate printed study information; (2) contacting potential subjects in person in the clinic, which has been shown to be preferred over unsolicited telephone calls  and to be more effective in recruiting minority subjects; and (3) providing participant incentives of \$20.00 for every assessment completed (\$40.00 for both) to offset subject burden.

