ANCOVA, to compare the effects of cognitive training to attention control will be used. The dependent variables, cognitive performance measured post-intervention, will be the primary outcomes. The baseline cognitive performance will be adjusted for as a covariate. The other independent variables will be the fixed effect for training group (BrainHQ, attention control), the Time effect, and the interaction term of Time-by-Training Group. The primary test of interest will the Group effect, which compares the two randomized groups on the outcome. The second most important test will be the interaction test to determine whether change over time differs for the two groups. We will also assess the Time effect, which tests whether scores generally changed in one direction for both groups combined. In addition, to ensure equivalence across groups potential covariates will be adjusted for in the models on which the various intervention and control groups significantly differ after random assignment at a liberal p-value of <.10. Effect sizes between the two groups will be computed as differences between adjusted means divided by pooled standard deviations. The significance level will be <.05 for all tests of hypotheses. Aim 5 provides the estimation of the effect of cognitive training on serum BDNF. Similar to Aims 1 and 2, a GLMM will be fitted to the data to estimate this effect, while controlling for potential known confounding effects including, age, education, smoking status, body mass index, medications, physical activity (per DUKE Activity Status Index) that may influence BDNF interpretation prior to hypothesis testing; although the RCT design will likely balance these factors.

**Power analysis:** We are adequately powered for estimating effect sizes or preliminary efficacy (Aim 2). Sample size is based on Aim 2 preliminary tests of post-intervention efficacy of the intervention on continuous outcomes. A difference between means equal to 0.80 standard deviations represents a large effect size, a medium effect size is 0.50, and a small effect size is 0.20.96 Using the Nquery software, a sample size of 30 in each group will provide 86% power for a two-sided t test to detect a large effect size of 0.80 when alpha is .05, to detect small or medium effect sizes.

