**Methods for Handling Missing Data and Dropouts:** The GLMM approach to analysis allows use of all available data, including from participants who have incomplete (i.e., partially missing) data. We will compare those who dropped out to those who completed the study on various demographic and treatment factors and on intervention group membership. To the extent that differences exist, we will describe this bias and its potential effects on the results of our analysis. Additionally, we will attempt to determine missing data patterns, and, if cell sizes permit, will incorporate this information into the analyses by re-running the GLMM with incorporation of the missing pattern as a nominal covariate.

Additionally, the influence of treatment dose (i.e.: sessions completed) will be evaluated to determine if it should be included as a covariate in the GLMM. Participants will be randomized only after completing baseline assessment. There are only two possible missing data patterns: baseline and immediate post only.

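### Section 10 lets training dose, which accrues after randomisation, enter the GLMM as a covariate and does not say that the model without dose stays primary

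*Combined protocol and SAP*

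**What the plan says.** All references are to the combined protocol and SAP.

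- **Section 10, Aims 2-4.** The mixed model contains baseline as a covariate, training group, time and their interaction, plus covariates on which the groups differ at p < .10. On the main test it says: "The primary test of interest will the Group effect, which compares the two randomized groups on the outcome".
- **Section 10, Methods for Handling Missing Data and Dropouts.** After describing a re-run of the GLMM with missing-data pattern as a covariate, it adds: "the influence of treatment dose (i.e.: sessions completed) will be evaluated to determine if it should be included as a covariate in the GLMM". It gives no rule for that decision and no label such as supportive or exploratory. It does not say which model is then primary.
- **Section 8.2, Monitoring Treatment Fidelity.** Dose is to be monitored with "computer software built within BrainHQ and Rescue Time software for the active attention control (total time on task"), and "These variables will be examined and used in the analysis". The role in the analysis is not specified.
- **Section 8.2, Cognitive Training.** The target is up to 40 hours over 10 weeks, and "any participants who do not complete the total of up to 40 hours will not be counted as deviations".
- **Section 9, Table 2.** Dose is listed as computer-recorded time per session.

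**The concern.** Baseline assessment comes first, then randomisation, then training. Dose is therefore an outcome of the assigned arm as well as of the woman's motivation and health. The documents give some reason not to presume equal uptake. In Table 1 the control's novelty entry reads "Feedback and rewards not provided, may incur some satisfaction on their own", whereas BrainHQ has feedback and rewards built in. Hypothesis 1 expects that "BCS assigned to the cognitive training arm will perceive the intervention as more acceptable and useful than BCS assigned to the attention control condition". Falling short of 40 hours is allowed.

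With dose in the model, the Group coefficient compares women at equal recorded dose, not the groups as randomised. If dose differs by arm and predicts outcome, that coefficient is shifted and the .05 level no longer holds. Section 10 also derives effect sizes from adjusted means, and the abstract says positive results will lead to a full-scale study. A shifted estimate could therefore be carried into the next trial's planning.

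**Working it through.** **The plan's own figure.** Two-sided t test, 30 per group, 0.80 SD, alpha .05 (section 10, Power analysis): noncentrality 0.80 × sqrt(30/2) = 3.10 on 58 df gives power 86.1%. The plan states 86%, so it reproduces.

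**Effect of adding dose.** Set the within-arm SDs of outcome and dose to 1. Let r be the within-arm correlation of dose with outcome, and d the arm gap in mean recorded dose, in SDs. The documents give neither, so both are assumptions. As in the plan's own power calculation, baseline is ignored.

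- Adjusted Group difference = unadjusted difference − r × d, with d positive when BrainHQ dose is higher.
- SE = sqrt[(1 − r²) × (2/n + d²/(2(n − 1)))], with n = 30 per arm and df = 2n − 3 = 57.

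For r = 0.3 and d = 0.5:

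- Shift = 0.3 × 0.5 = 0.15 SD, which is 0.15/0.80 = 19% of the planned effect.
- SE = sqrt[0.91 × (0.0667 + 0.0043)] = 0.254.
- No true effect: noncentrality 0.15/0.254 = 0.59 in size; type I error 8.9%.
- True effect 0.80, BrainHQ dose higher: expected estimate 0.65, noncentrality 0.65/0.254 = 2.56, power 71.0%.
- True effect 0.80, control dose higher: expected estimate 0.95. Nominal power rises to 95.7%, but the effect is overstated.

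The same formulas over a range of assumed values:

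| r | gap (SD) | shift (SD) | type I error | power at 0.80, BrainHQ dose higher | power at 0.80, control dose higher |
|---|---|---|---|---|---|
| any | 0 | 0 | 5% | no bias | no bias |
| 0.2 | 0.25 | 0.05 | 5.4% | 82.4% | 90.6% |
| 0.2 | 0.5 | 0.10 | 6.6% | 75.1% | 92.4% |
| 0.2 | 1.0 | 0.20 | 10.7% | 54.7% | 93.4% |
| 0.3 | 0.5 | 0.15 | 8.9% | 71.0% | 95.7% |
| 0.3 | 1.0 | 0.30 | 18.7% | 42.8% | 97.5% |
| 0.4 | 0.5 | 0.20 | 12.7% | 67.6% | 98.1% |
| 0.4 | 1.0 | 0.40 | 31.6% | 31.6% | 99.4% |

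**With baseline in the model.** A simulation of ANCOVA on group and baseline (30 per arm, 5,000 runs per setting) assumed a baseline coefficient of 0.6 and an unmeasured trait worth 0.5 SD of outcome that correlates 0.3 to 0.5 with dose. There was no true effect. Without dose in the model, rejection was 4.5% to 5.2%. With dose, a 0.5 SD gap gave bias of 0.08 to 0.13 SD and rejection of 6.1% to 9.2%. A 1 SD gap gave 0.15 to 0.25 SD and 9.7% to 20.7%. The bias had the opposite sign to the gap. With no gap, rejection was 4.9% to 5.0%.

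**Does evaluating dose first protect the test?** Suppose dose is added only when its own slope has p < .05 (an assumed rule, since the plan gives none). At r = 0.3 and d = 0.5, type I error is still about 9%. Selecting dose because it predicts outcome picks out the case in which it causes bias.

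**The case against.** The strongest reply is that the primary model is written out in section 10 without dose, and its Group test is described as comparing the randomised groups. Dose appears only under missing data, straight after a re-run of the GLMM, and the plan commits only to evaluating it. A supportive check may well be what was meant. This stands as far as it goes: a reader might infer that the primary analysis is already dose-adjusted, and the documents do not say that. But the dose sentence refers to inclusion in the GLMM itself, not to a re-run, and nothing keeps the model without dose primary.

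Three further readings are tempting and go too far.

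- **That dose is a different variable in each arm because the recording tools differ.** The split between BrainHQ software and Rescue Time is stated for total time on task. Section 8.2 also says both programs capture date and time of participation, which might supply session counts in both arms.
- **That dose has three conflicting definitions.** Time per session sums to total time on task. The real difference is between hours (sections 8.2 and 9) and session count (section 10).
- **That one common slope will equate crossword time with BrainHQ time.** The control was chosen partly because "it has not shown cognitive benefit in previous research studies", so a common slope would be doubtful. The plan, however, does not state the form of the dose term.

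On size, nothing in the documents supports a gap as large as 1 SD. Both arms have the same schedule of 4 hours a week for 10 weeks, and Hypothesis 1 concerns perceived acceptability, not hours used. Conditional inclusion also softens the power loss: at r = 0.2 and a 1 SD gap, power is about 70% under the p < .05 rule, against 54.7% if dose is always included.

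**Conclusion.** The point holds as a minor one. As written, section 10 permits a data-driven step that could put a post-randomisation variable into the model carrying the primary test, with no statement that protects the randomised comparison. Harm requires three things together: dose is added to the reported model, mean recorded dose differs by arm, and dose is related to outcome. If mean dose is equal there is no bias, and the GLMM without dose is unaffected in any case.

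The illustrative size at r = 0.3 and a 0.5 SD gap is a shift of 0.15 SD and type I error of about 9%, and the direction of the shift is not known. These figures rest on assumed r and d and on a calculation without the baseline covariate. They show that the effect could matter, not how large it will be. A reader might infer from the bottom row of the table that power will collapse to about 32%. The documents give no support for those values, and with control dose higher the same model overstates the effect instead.

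**What to change.** In section 10, state that the primary Group test comes from the GLMM without dose, whatever the dose evaluation shows. Report recorded dose by arm descriptively. Label any dose-outcome or dose-adjusted model exploratory, and do not read it as the randomised effect. Choose one dose measure, hours or sessions, and use it in sections 8.2, 9 and 10.

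This takes a few sentences and needs no added data, visits or participants. The plan's 86% power figure does not change. What is given up is that a dose-adjusted group estimate can no longer be the primary result.

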#### 11. DATA INTEGRITY AND SECURITY

All documentation will be stored on a limited-access university server or in locking file cabinets in a limited-access, locked project office. All electronic databases housing subject data will be password-protected with access limited to study personnel only. Identifying information is separated from all data provided by participants through the use of a unique identification code assigned by study personnel to each subject.

Analysis of objective neuropsychological data will be monitored for quality assurance. Personnel who conduct the neuropsychological assessments (tester) will complete a standardized

instruction course and will be certified to deliver the assessment based on criteria developed by [name] (Co-I).

All data entry will be done by trained personnel. Databases will be constructed to include forms for data entry that mirror questionnaires and have restricted field ranges and values to prevent errors. In addition, quality of data entry will be monitored by the Project Manager, who will randomly select patient files to be double-entered and will periodically generate reports for the entire dataset to identify outliers, missing data, or other problems. All data will be imported into SAS data sets for analysis. Analyses will include only summaries of data; personal identifiers will be omitted

## 12. STUDY TIMELINE

Study Timeline	May	June	July	Aug	Sept	Oct	Nov	Dec	Jan	Feb	Mar	Apr
Study start up (hiring, training, finalize all study protocols)	Х											
Enrollment and baseline data collection		Х	X	Х	Х	Х	Х	Х	Х			
Randomization, delivery of intervention/control		Х	X	Х	Х	Х	Х	Х	Х	Х		
Follow-up data collection, data entry and management		Х	X	Х	Х	Х	Х	Х	Х	Х	Х	
Analyze preliminary, baseline and follow-up			X	X	Х	Х	Х	Х	Х	Х	Х	Х
Dissemination: literature review, theory review, intervention description, baseline and final study findings			X	X	X	Х	Х	X	Х	X	Х	Х

# 13. RISKS TO SUBJECTS

Potential risks associated with study participation are minimal. Subjects may experience: (a) bruising, bleeding, soreness or rarely, fainting of infection as a result of venipuncture for collection of the blood samples (b) psychosocial risks and (c) breach of confidentiality. Risks in the psychosocial realm would involve any anxiety or distress that may result from participation in the scheduled study assessments and/or phone interview. Based on our prior work with similar assessment protocols, we anticipate that any negative psychological reactions will be uncommon and generally very mild. There is always some risk that a woman's responses during the study will become known to others outside the research project staff. No unusually sensitive information is being collected in our study; for example, we are not collecting information on sexual behavior or criminal behaviors, or substance abuse.

Steps will be taken to minimize any potential risks associated with study participation.

To minimize bruising, bleeding, soreness or rarely fainting or infection as a result of venipuncture. Our experienced research staff is trained and certified in phlebotomy. They will apply universal precautions when drawing blood to reduce the risk of infection and will take steps to minimize discomfort to subjects including application of pressure on the site following

needle withdrawal. Additionally, subjects will be asked to remain in a sitting position for five minutes after blood has been withdrawn and will be observed for any untoward effect.

**To minimize any psychosocial or physical risks**, participants will be told that they have the option of discontinuing their study participation at any time during the course of an assessment session or at any point during the study. Research assistants will be trained to identify unusual distress and will notify the PI, who will conduct follow-up assessments and refer participants to their healthcare provider if necessary.

To minimize risks associated with breach of confidentiality we will assign each study participant a unique identification number and using this to identify all study data records. A single list connecting the study identification number with each participant's name will be kept in a password-protected database on a limited-access university server. Furthermore, all study data records, or digital recordings will be maintained in locked file cabinets and/or password-protected databases on limited-access university servers. Access to study data records will be furnished only to individuals who are members of the project research team. All personnel who are involved in the design or conduct of this research will have successfully completed human subjects training.

For women who exhibit extreme scores on the PHQ-9 brief depression screen we will adhere to the following PHQ-9 Referral Algorithm: Score  $\geq$  15, negative response to self-harm item: Refer to physician for follow-up; Score  $\geq$  15 positive response to self-harm item: Keep patient on the telephone, assess emergent needs of patient. If immediate risk is low, refer to suicide hot line and inform patient you will be notifying her oncologist for follow-up. If immediate risk is high, call 911, refer to suicide hot line, and inform patient you will be notifying her oncologist for follow-up.

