#### 6.2 Exclusion criteria

- 1. Comorbidities that would sufficiently impair performance or inhibit cognitive training such as: history of stroke, encephalitis, traumatic brain injury, brain surgery, dementia, or Alzheimers disease.
- 2. Cranial radiation or intrathecal therapy.
- 3. Current active major depression or substance abuse or history of bipolar disorder psychosis, schizophrenia, or learning disability.
- 4. History of current or other cancer except for basal cell skin cancer.

No potential participant will be excluded due to not having a computer. The study will provide a computer tablet with data capability to ensure access to participate. This need is not estimated to be high as the most recent Census data identified that 84% of U.S. households own a computer and 73% have a computer with a broadband connection to the internet.

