#### Introduce study and screen for eligibility/interest

For in clinic recruitment, the project recruiter then sequentially approaches each woman at the end of her clinic visit with the physician and describes the purpose and nature of the study.

For those that contact our office in response to a mailing, study staff will discuss the study requirements and screen for eligibility (phone or in person. Those determined to be ineligible due to depressive symptoms will be referred to their attending physician for follow-up.

**Distribute study information:** Following screening, study staff will send or hand out a study packet. Packets will contain a cover letter with contact information; a study brochure; copies of the informed consent statement and HIPAA-mandated authorization to allow use of protected health information; and a stamped, addressed envelope for returning the signed consent and authorization forms.

**Obtain informed consent:** Women who are eligible and interested will be consented in person in the clinic. Those women who do not return a signed consent will receive a phone call one week following their screening date to verify interest in participating and provide additional information if needed. Interested women will be instructed on the consent process. Informed consent will follow the requirements of the university's institutional review board

**Eligibility/Baseline Assessment:** After the signed written consent and HIPAA authorization forms are received, research staff will telephone the participant and arrange a mutually convenient appointment. Assessments will be completed in a private room at the university. First, eligibility will be confirmed via self-report by the participant.

If ineligible, the subject will be thanked for her time and interest in participating.

If eligibility is confirmed, the appointment will continue, and the other baseline assessment measures will be administered. Once the neuropsychological assessment and questionnaires are completed, the tester will review them and obtain data from the participant on any missing items

**Randomization:** Building on our pilot studies, BCS will be randomly assigned to one of two groups: BrainHQ cognitive training or attention control. Assignments will be in a random order generated by a computer using blocks of 8, to ensure filling of treatment groups. Randomization will occur as close to the start of the training sessions as possible to minimize study drop-out.

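### The PHQ-9 referral algorithm gives no step for a positive self-harm answer when the total score is below 15

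*Combined protocol and SAP*

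**What the plan says.** The rule is in Section 13 (Risks to Subjects). Its opening limits who it applies to: "For women who exhibit extreme scores on the PHQ-9 brief depression screen we will adhere to the following PHQ-9 Referral Algorithm". Two branches follow, each with its own condition that the total is at least 15.

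- Negative self-harm answer, at a score of at least "15, negative response to self-harm item: Refer to physician for follow-up".
- Positive self-harm answer, at a score of at least "15 positive response to self-harm item: Keep patient on the telephone, assess emergent needs of patient". If the immediate risk is judged low: "If immediate risk is low, refer to suicide hot line and inform patient you will be notifying her oncologist for follow-up". If it is judged high, staff also call 911.

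Two other provisions come near this situation. Section 8.1, on introducing the study and screening, states: "Those determined to be ineligible due to depressive symptoms will be referred to their attending physician for follow-up". Section 13 also has a general distress procedure, under which research staff "identify unusual distress and will notify the PI, who will conduct follow-up assessments and refer participants to their healthcare provider if necessary".

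The related exclusion in Section 6.2 reads "Current active major depression or substance abuse". It names no PHQ-9 cut-off and does not mention the self-harm item.

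**The concern.** The algorithm is a participant-safety rule, and its emergency response depends on two conditions at once: a positive self-harm answer and a total of at least 15. Staff who follow it exactly could ask the self-harm question, hear a positive answer, find a total below 15, and have no step to take. Risk assessment, hot line referral and notice to the oncologist would then rest on individual judgement, or on a provision that responds to something other than the answer. What is at stake is a self-harm disclosure that the study itself elicits and then does not assess.

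**Working it through.** No power, alpha or sample-size figure bears on this point, so the check is one of logic. Cross the two conditions that the algorithm uses and look for a stated action in each case.

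| Total score | Self-harm answer | Action stated in the Section 13 algorithm |
|---|---|---|
| At least 15 | Negative | Physician referral |
| At least 15 | Positive | Stay on the line and assess; hot line and oncologist notice; 911 as well if risk is high |
| Below 15 | Negative | None (none evidently needed) |
| Below 15 | Positive | **None** |

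Actions are stated for 2 of 4 cases. Of the 2 cases with a positive answer, 1 has an action and 1 does not.

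Comparing the first two rows shows what the self-harm answer does. At the same total, a negative answer leads to a routine referral and a positive one to an immediate risk assessment. The answer, not the total, separates the two responses. Yet a woman with a total of 15 who denies self-harm is referred, while a woman with a total of 14 who affirms it meets no step.

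Next, does any other text fill the empty case?

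1. **Referral at screening (Section 8.1).** It applies only once a woman has been ruled ineligible for depressive symptoms. Section 6.2 gives no PHQ-9 score or self-harm rule that would produce that ruling. Where it does apply, it gives a physician referral without an immediate risk assessment.
2. **Distress procedure (Section 13).** It depends on staff identifying distress and is not tied to the PHQ-9 or its self-harm item. It is written for participants and concerns distress arising from the scheduled assessments or the phone interview. Table 2 in Section 9 lists the PHQ-9 under screening. For women who respond to a mailing, Section 8.1 places screening before the consent packet is sent. Whether the procedure reaches a woman on a screening call is unclear.

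No other text in the documents names the self-harm item. Nor does the gap look like damage from text extraction: the threshold is written separately in each branch, and the text runs on to the end of the section.

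**The case against.** The strongest reply accepts the literal reading and disputes its consequence.

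- **Scoring.** The gap matters only if a positive self-harm answer can occur with a total below 15, and the documents give no PHQ-9 item scoring or range. This stands as an assumption that has to be stated. The algorithm supports it by treating the answer and the total as separate conditions.
- **Related safeguards.** Both general provisions concern the same kind of problem, and staff could reasonably treat a disclosed self-harm answer as distress to be reported. That softens the practical effect. It does not supply the missing step, because neither provision is triggered by the answer.
- **Limited exposure.** Table 2 schedules the PHQ-9 once, under screening, and does not repeat it at T2. This stands: the gap arises at one contact and not throughout follow-up.
- **Undefined term.** The algorithm does not say what counts as a positive answer, and a fix that makes the answer the sole trigger relies more heavily on that term. This is fair, and is best settled in the same edit.
- **Cost.** Section 15 requires IRB approval of protocol changes. Notifying more oncologists may also mean more disclosures about women who have not yet consented. Both are real costs. The existing branch already accepts such disclosure at a score of 15 or more.

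None of these points gives the missing case an action.

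**Conclusion.** The concern holds. The algorithm states no step for a positive self-harm answer with a total below 15, and no other provision is triggered by that answer. The gap is one of the two positive-answer cases, and the number of women in it cannot be derived from the documents. The textual gap is certain. Its practical effect rests on the scoring assumption and on how staff would apply the two general provisions. No estimand, analysis or sample size is affected. As a safety rule with a simple remedy, it should be corrected.

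**What to change.** In Section 13, drop the score condition from the positive-answer branch and keep it only for the negative-answer referral. Widen the opening sentence so that it also covers any woman who answers the self-harm item positively. The revised rule would read, in substance:

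- *Total of at least 15 with a negative self-harm answer: physician referral, as now.*
- *Positive self-harm answer at any total: keep the woman on the telephone or, if she is present, with staff, and assess her immediate needs. Then follow the existing low-risk or high-risk steps unchanged.*

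The in-person wording is a minor clarification. Section 8.1 lets staff "screen for eligibility (phone or in person", and the documents do not say how the PHQ-9 itself is given. The same edit should state which answers count as positive.

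The cost is a short amendment with IRB approval, a staff instruction, and an unknown number of additional risk assessments and oncologist notifications, some possibly before consent. Sample size, randomisation and analysis are unchanged.
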